### 10.3 SAMPLE SIZE CONSIDERATIONS

It is difficult to recruit a large number of patients diagnosed with schizophrenia with persistent auditory hallucinations to participate in a single site extensive study. However, based on our recent experience recruiting for patients with these symptoms, we expect that we can successfully recruit 40 subjects from this population.

We evaluated the performance characteristics of the study design and analysis strategy under the assumption that only 40 subjects will be available. To do this we used information from a previous randomized study conducted in this lab (IRB 14-3285). That study obtained baseline AHRS scores ( $Y_0$ ) and post-treatment AHRS scores ( $Y_1$ ) from participants sampled from our target population using the same methods and inclusion/exclusion criteria.

**Table 2** lists information obtained: 7 patients received sham treatment (**S**), 8 received 10Hz tACS treatment (**A**).

Based on **Table 2** estimates for AHRS, we anticipate that 20 participants per regimen in period 1 will provide a margin of error of about 1.0 AHRS unit for regimen-specific estimates of mean change from baseline; i.e., we anticipate a 95% C.I. of the form [mean change  $\pm$  1.0] for each regimen.

For the primary analysis, the model will be fitted using only AHRS scores at  $t \in \{t_1, t_0\}$ :

$$E[\Delta Y_{ij}(t) | X, Y_{ij}(t_0)] = \mu_S X_1 + \mu_A X_2 + \tau_S X_3 + \tau_A X_4 + \beta (Y_{ij}(t_0) - \bar{Y}(t_0))$$

We will test  $H_0: "(\mu_S - \mu_A) = 0 \text{ and } (\tau_S - \tau_A) = 0"$ , using an F-test of size  $\alpha = 0.05$ . However, for purposes of the analysis of anticipated power, we considered a close surrogate: testing  $H_0: "(\mu_S - \mu_A) = 0"$  and  $H_0: "(\tau_S - \tau_A) = 0"$  separately using F-tests each of size  $\alpha = 0.025$ . In **Figure 2**, power curves are for the test of  $H_0: "(\mu_S - \mu_A) = 0"$ .

The curves are based on the point-estimates and 95% C.I. estimates of intra-subject and inter-subject variance components expressed here as standard deviations (by taking square roots) which are in turn based on the data in Table 2 and based on a conjectured underlying correlation of 0.90 between  $t_0$  and  $t_1$ .

[figure not shown]
[figure not shown]
The probability ('power') of drawing a sample that yields a p-value  $< \alpha = 0.025$  is a function of the unknown magnitude of the treatment effect ( $\mu_S - \mu_A$ ) in the target population. In **Figure 2**, for example, if our conjectures and assumptions are true and in truth  $(\mu_S - \mu_A) = 1.18$  AHRS units, the likelihood of rejecting  $H_0: (\mu_S - \mu_A) = 0$ " is estimated to be 90% with C.I. [50%, 99%]. For comparison, **Figure 1** provides power curves for a test of  $H_0: (\mu_S - \mu_A) = 0$ " based on only the data from period 1 --an approach that does not take advantage of the crossover design.

**Figure 3** provides similar information for test of  $H_0: (\mu_S - \mu_A) = 0$ " based on AHRS scores recorded on occasions  $t \in \{t_1, t_6, t_7, t_8, t_9\}$  assuming carryover effect  $\lambda$  has vanished before  $t_6$ . Inclusion of the carryover effect in the model can reduce precision and power for the test of treatment effects.

When exploring carryover effects using scores from occasions  $t \in \{t_1, t_2, t_6, t_7, t_8, t_9\}$  to fit

$$E[\Delta Y_{ij}(t) | X, Y_{ij}(t_0)] = \mu_S X_1 + \mu_A X_2 + \tau_S X_3 + \tau_A X_4 + \lambda X_5 + \beta (Y_{ij}(t_0) - \bar{Y}(t_0)),$$

the power curves in **Figure 4** indicate anticipated power levels for a test of  $H_0: (\mu_S - \mu_A) = 0$ " when it is assumed that carryover impacts the score at  $t_2$  but not the scores at  $t_6, t_7, t_8$  and  $t_9$ .

It is anticipated that some participants will have incomplete data. **Figures 5, 6, 7 and 8** indicate the performance of the test procedures when the sample size is reduced to 30 participants. (Compare to Figures 1, 2, 3 and 4).

**Figures 1 - 8** were computed using the ability of SAS PROC MIXED to calculate the non-centrality parameter of the distribution of the F-statistic for a completely specified linear mixed-effects model. The resulting power-curve estimates are conjectures based on 1) previous data from only 15 subjects, 2) assumptions about the appropriate model for the data, 3) an assumption that the variance components have the same magnitudes for treatments S and A, and 4) an assumption that the correlation coefficient for the model's compound-symmetry covariance structure is 0.90.

In summary, based on considerations of anticipated precision of estimators, anticipated power levels of test procedures, anticipated availability of research subjects, and stage of this line of research, we anticipate the study is likely to achieve its specific aims; i.e., there is low risk the study will be uninformative and inconclusive.

The follow-up case study will be used to assess feasibility of long-term maintenance. The sample size is low as we do not intend to perform statistical analysis on outcomes. This observational study will be used to inform future, large-scale studies evaluating treatment efficacy of this intervention.

Figure 5 EY\_1

[figure not shown]

Figure 6 EY\_1\_9

[figure not shown]

Figure 7 EY\_1\_6789

[figure not shown]
[figure not shown]

Figure 8 EY\_1\_2\_6789

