### **4 STUDY DESIGN AND OUTCOME MEASURES**

#### **4.1 STUDY OUTCOME MEASURES**

##### **4.1.1 PRIMARY OUTCOME MEASURES**

The Auditory Hallucination Rating Scale (AHRS) will be the primary outcome measure for this study. This survey instrument will be administered at the first recruitment visit, two weeks later at the screening visit, at baseline ( $t_0$ ) on the first day of stimulation, after stimulation on the fifth day of stimulation ( $t_1$ ), and at each of the 8 weekly maintenance sessions ( $t_2, t_3, t_4, t_5, t_6, t_7, t_8, t_9$ ). The primary analyses will focus on longitudinal changes from baseline in the AHRS scores at  $t_1$  and  $t_9$  accounting for the following explanatory variables: treatment regimen, treatment stage (initial daily stimulation vs maintenance weekly stimulation), and the baseline AHRS score as a covariate.

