For AHRS,  $Y_{ij}(t_0)$  is the baseline score from the  $i$ -th participant in the  $j$ -th treatment sequence ( $j = SS, SA, AS, AA$ ). The primary analyses will focus a linear mixed-effects model for the change from baseline on occasion  $t$ ,  $\Delta Y_{ij}(t) = Y_{ij}(t) - Y_{ij}(t_0)$ , conditional on the following explanatory variables: assigned treatment regimen, treatment stage (initial daily stimulation vs maintenance weekly stimulation), and baseline score  $Y_{ij}(t_0)$  as a covariate.

$$[\Delta Y_{ij}(t) | \mathbf{X}, Y_{ij}(t_0)] = \mu_S X_1 + \mu_A X_2 + \tau_S X_3 + \tau_A X_4 + \lambda X_5 + \beta (Y_{ij}(t_0) - \bar{Y}(t_0)) + \varepsilon_i + \varepsilon_{ij}(t)$$

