**Table 1. Conditional expected value of change from baseline evaluated at the average baseline value**

		Treatment Sequence			
		SS	SA	AS	AA
Period 1	$t_1$	$m_S$	$m_S$	$m_A$	$m_A$
	$t_2$	$m_S + \tau_S$	$m_A + \tau_A$	$m_S + \tau_S + \lambda$	$m_A + \tau_A + \lambda$
	$t_3$	$m_S + \tau_S$	$m_A + \tau_A$	$m_S + \tau_S + \lambda$	$m_A + \tau_A + \lambda$
	$t_4$	$m_S + \tau_S$	$m_A + \tau_A$	$m_S + \tau_S + \lambda$	$m_A + \tau_A + \lambda$
	$t_5$	$m_S + \tau_S$	$m_A + \tau_A$	$m_S + \tau_S + \lambda$	$m_A + \tau_A + \lambda$
	$t_6$	$m_S + \tau_S$	$m_A + \tau_A$	$m_S + \tau_S$	$m_A + \tau_A$
	$t_7$	$m_S + \tau_S$	$m_A + \tau_A$	$m_S + \tau_S$	$m_A + \tau_A$
	$t_8$	$m_S + \tau_S$	$m_A + \tau_A$	$m_S + \tau_S$	$m_A + \tau_A$
	$t_9$	$m_S + \tau_S$	$m_A + \tau_A$	$m_S + \tau_S$	$m_A + \tau_A$

For the primary analysis, the above model will be fitted using only AHRS scores at  $t \in \{t_1, t_9\}$  assuming  $\lambda=0$ :

$$E[\Delta Y_{ij}(t) | \mathbf{X}, Y_{ij}(t_0)] = \mu_S X_1 + \mu_A X_2 + \tau_S X_3 + \tau_A X_4 + \beta (Y_{ij}(t_0) - \bar{Y}(t_0))$$

The set of sensitivity analyses will include fitting the model using AHRS scores at  $t \in \{t_1, t_6, t_7, t_8, t_9\}$  (with  $\lambda=0$ ), which is anticipated to provide more precision and power for analysis of the treatment effects.

The analyses will focus on the point estimates and confidence interval estimates of the parameters of interest; for example,  $(\mu_S - \mu_A)$  and  $((\mu_S + \tau_S) - (\mu_A + \tau_A))$ . The data and the fitted model will be visualized via graphical figures. The fitted model using only AHRS scores at  $t \in \{t_1, t_9\}$  will be used to test the primary null hypothesis,  $H_0: "(\mu_S - \mu_A) = 0 \text{ and } (\tau_S - \tau_A) = 0"$ , using an F-test of size  $\alpha = 0.05$ .

To explore carryover of treatment effects, the model

$$E[\Delta Y_{ij}(t) | \underline{X}, Y_{ij}(t_0)] = \mu_S X_1 + \mu_A X_2 + \tau_S X_3 + \tau_A X_4 + \lambda X_5 + \beta (Y_{ij}(t_0) - \bar{Y}(t_0))$$

will be fitted using AHRS scores recorded on occasions  $t \in \{t_1, t_2, t_3, t_4, t_5, t_6, t_7, t_8, t_9\}$ .

Sensitivity analyses will be used to evaluate the robustness of the main results to reasonable perturbations of the methods and assumptions used. This set of analyses will examine goodness of fit diagnostics for the linear model, and will include modified versions of the main analyses.

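### The primary model gives day 5 and week 8 one residual variance; if AHRS given baseline is more variable at week 8, the week-8 interval is too narrow and the week-1 interval too wide

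*Combined protocol and SAP*

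**What the plan says.** Section 10.2, Aim 1: "The primary analyses will focus a linear mixed-effects model for the change from baseline". The equation carries a participant effect, an occasion-level residual and a single coefficient β on centred baseline. Section 4.1.1 likewise lists regimen, stage "and the baseline AHRS score as a covariate", with no baseline-by-stage term. Section 10.3 lists, among the assumptions behind its power curves, that the correlation under the "compound-symmetry covariance structure is 0.90".

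For the primary analysis the model is restricted to t1 and t9 with λ = 0. On testing, section 10.2 says of the fit to those two occasions that it "will be used to test the primary null hypothesis". That hypothesis is joint: (μS − μA) = 0 and (τS − τA) = 0, by an F-test at 0.05. In section 10.3 the two parts are tested "separately using F-tests each of size" 0.025, but only as a surrogate for the power calculation.

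On estimation: "The analyses will focus on the point estimates and confidence interval estimates of the parameters of interest". The two examples given are the week-1 effect (μS − μA) and the week-8 effect (μS + τS) − (μA + τA).

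Table 2 conjectures equal variances for sham and active treatment. Nothing is said about equal variances across occasions. Table 2 has baseline and one post-treatment score from 15 people, and section 10.3 ties the 0.90 to t0 and t1.

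**The concern.** Day 5 is less than a week after baseline. Week 8 falls eight or nine weeks after day 5, depending on whether the gap week of section 7.4.3 is counted. If scores track baseline less closely by then, the week-8 change has a larger variance given baseline and a different baseline slope. A random-intercept fit averages the two variances and gives both contrasts the same standard error, which is too small for week 8 and too large for week 1.

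These contrasts answer the two clinical hypotheses of section 10.1: that daily stimulation reduces symptoms, and that the maintenance regimen extends the benefit. Section 10.2 puts the weight on their intervals rather than on p-values. An interval for maintenance that is too narrow and one for the initial week that is too wide would distort the trial's main output. Section 10.2 expects to carry the same model to PANSS, BACS and EEG alpha power.

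**Working it through.** **Inputs.** From Table 2: AHRS variance 29.10 (SD 5.39), baseline–day-5 correlation 0.90, inter- and intra-subject conditional variances 4.98 and 0.55. N = 40, 10 per sequence. Assumed, because no document gives them: r, the correlation of week 8 with baseline, and q, that of week 8 with day 5.

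**1. The plan's own figure.** With four equal sequences and λ = 0, the two periods' assignments are orthogonal. The variance of a treatment contrast is then 4v(1 − ρ²)/N, where v is the variance given baseline and ρ the t1–t9 correlation given baseline. Here v = 4.98 + 0.55 = 5.53 and ρ = 4.98/5.53 = 0.90, so SE = √(4 × 5.53 × 0.19/40) = 0.324. At a difference of 1.18, α = 0.025 and 37 denominator df, power is 90%. The variance limits give 99% and 50%. This reproduces the stated 90% [50%, 99%].

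**2. Conditional moments if the week-8 correlations differ.** v1 = 29.10(1 − 0.90²); v9 = 29.10(1 − r²); covariance c = 29.10(q − 0.90r).

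| r = q | v1 | v9 | c | ρ |
|---|---|---|---|---|
| 0.9 | 5.53 | 5.53 | 2.62 | 0.47 |
| 0.8 | 5.53 | 10.48 | 2.33 | 0.31 |
| 0.7 | 5.53 | 14.84 | 2.04 | 0.22 |

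**3. What the common-variance fit reports.** The common slope misses each occasion's slope by (0.90 − r)/2. This adds e = 29.10 × ((0.90 − r)/2)² to each variance and subtracts it from the covariance. The pooled variance is v = (v1 + v9)/2 + e and the pooled correlation is k = (c − e)/v. The reported SE for both contrasts is √(4v(1 − k²)/40). The true week-8 SE is √(0.1[(v9 + e) − 2k(c − e) + k²(v1 + e)]). Exchange v1 and v9 for week 1.

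| r = q | e | v | k | Reported SE | True SE, week 1 | True SE, week 8 |
|---|---|---|---|---|---|---|
| 0.8 | 0.07 | 8.08 | 0.28 | 0.863 | 0.719 | 0.986 |
| 0.7 | 0.29 | 10.48 | 0.17 | 1.009 | 0.752 | 1.213 |

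The 37-df critical value is 2.026. At r = 0.8, week-8 coverage is P(|t| < 2.026 × 0.863/0.986) = P(|t| < 1.77), about 91.6%. At 0.7 it is P(|t| < 2.026 × 1.009/1.213) = P(|t| < 1.69), about 90%.

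**4. Simulation with REML fits (N = 40, 37 df).** Several independent runs under the null agree with step 3. The week-8 contrast is excluded from its nominal 95% interval 7.9–9.5% of the time at 0.8 and 9.4–10.6% at 0.7. The week-1 contrast is excluded 1–3% of the time. At 0.8 the mean reported SE is 0.854 for both contrasts, against 0.70 and 0.97 with unstructured covariance and separate slopes.

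Week-1 power at α = 0.05 for 3.75 − 2.29 = 1.46 units, the Table 2 difference:

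| r = q | Planned model | Unstructured, separate slopes |
|---|---|---|
| 0.9 | 58–59% | 55–58% |
| 0.8 | 35–37% | 51–52% |
| 0.7 | 26–27% | 51–52% |

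**5. The joint primary F-test.** Null rejection is 5.1% at 0.8 and 5.8% at 0.7; a smaller check put it at about 5–7%. With a 1.18-unit effect at week 1 only, its power is about 18% v 29% at 0.8 and 13% v 28% at 0.7 (planned v unstructured). The test of (τS − τA) alone stays at 5.1% and 4.7%.

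**6. Which restriction does the damage.** With unequal variance alone (5.53 v 14.84, same slope), null rejection is 9.9% at week 8 and 0.9% at week 1. With unequal slope alone (0.9 v 0.7, same variance), it is 5.1% and 4.8%, and week-1 power at 1.18 units falls only from 43% to 39%.

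**7. The plan's conditional correlation kept at 0.90.** The raw correlation of 0.9 in step 2 implies ρ = 0.47, which is not the plan's power model. Keeping ρ = 0.90 and changing only week 8 gives week-8 null rejection of 6.9% (v9 = 10.48, slope 0.8) and 8.3% (v9 = 14.84, slope 0.7). Week-1 power at 1.18 units and α = 0.025 is then 54% and 22%, against 89% with the alternative. The direction is the same.

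**The case against.** The strongest objection is that the plan's only formal test is the joint F-test, and step 5 shows its size is essentially intact. A reader might infer that the primary analysis has an inflated false-positive rate, or that a maintenance test rejects at 9–10%. The documents support neither, because no separate week-8 test is named. What remains is interval coverage and lost power.

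A reader might also infer that any drift in AHRS by week 8 causes the trouble. It does not, since τS and τA absorb a shift in the mean. Only a change in variability given baseline matters for coverage.

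The week-8 correlations are assumptions. Table 2's note that the correlation could plausibly lie between 0.56 and 0.99 reflects uncertainty about one correlation, not decay over time. Participants are also selected for stability: at most 20% AHRS change over two weeks and 12 weeks of clinical stability. This stands. The calculations show sensitivity and do not forecast. If week 8 were less variable than day 5, the distortion would reverse.

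The equation does not state that the residual variance is constant over occasions. That is true, but section 10.3 names compound symmetry as the model's structure and section 10.2 treats the intra-class correlation as a parameter. If another structure is intended, the plan should say so.

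Section 10.2 also promises fit diagnostics and modified analyses, and a review of the plan before data collection. These help, but none names unequal variance or a baseline-by-stage term. A structure chosen after seeing the data would weaken the pre-specification that the section sets out to secure.

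**Conclusion.** The concern holds for the two planned intervals and for power. If AHRS given baseline is more variable at week 8 than at day 5, the week-8 interval covers about 90–92% instead of 95% and the week-1 interval is too wide. Week-1 power for 1.46 units is about 36% or 27%, against about 52%. These figures assume week-8 correlations of 0.8 or 0.7 with both baseline and day 5, a baseline–day-5 correlation of 0.90, SD 5.39 and 40 complete participants. The common variance is the main cause; the common slope adds a small loss of efficiency.

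The power figures should not be read as a correction of the plan's 90%. That figure reproduces under the plan's own assumptions, and the scenarios here use a different conditional correlation, effect size and α.

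**What to change.** For the {t1, t9} primary model, pre-specify an unstructured 2×2 within-subject covariance, or one with a separate variance for each occasion. Add a baseline-by-stage term and a small-sample degrees-of-freedom method such as Kenward-Roger. Use the same form for PANSS and BACS. Compound symmetry can stay as a sensitivity analysis.

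The cost is two extra parameters (one covariance, one slope) and slightly fewer error degrees of freedom. If compound symmetry holds, the loss of power is at most a few points: 58–59% v 55–58% in step 4, and 90.4% v 89.5% under the plan's own power model at 1.18 units. The unstructured fits were run with a fixed 37 df and rejected 4–7% of the time under the null, which is why a small-sample adjustment is advised. Kenward-Roger itself was not simulated, and nothing was calculated for PANSS or BACS.

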## 10.4 RANDOMIZATION AND BLINDING

### 10.4.1 ENROLLMENT/ RANDOMIZATION/ MASKING PROCEDURES

Participants will be randomized into one of four treatment-sequence groups. The randomization assignment will occur prior to beginning the initial 5 days of stimulation, once the participant has passed the screening sessions. The randomization will be as follows: tACS and tACS, tACS and sham, sham and sham, sham and tACS. This is a double blind study, so neither the participant nor the researcher will know which treatment treatment-sequence group the participant has been assigned to.

A [name] Lab member ([name]) will randomize 40 codes which will be used by the study coordinator and research assistants. These codes will be randomized prior to recruitment of any participants. These codes are directly linked to which treatment regimens the participants receive (sham (S) or 10Hz tACS (A)).

The codes will be randomized using a randomization function available in MATLAB software. A condition will be included so that the same condition will not be assigned to adjacent participants 3 times in a row. The participant randomization will also be stratified on sex, in that separate randomization schedules will be created for each sex. A total of 40 codes will be randomized for each sex because it is possible that there will be, for example, 35 men and only 5 women.

[name] will have no other responsibility in the study other than providing these randomized codes. The master list containing the condition and the codes will be kept solely by [name].

[name] will provide the study coordinators an Excel document with the blinded randomized codes. This document will remain on the secure lab drive. The study coordinator will enter the participant's study ID next to their randomization code on the first day of stimulation.

(The CONSORT Statement notes that "Allocation concealment is a technique used to prevent selection bias by concealing the allocation sequence from those assigning participants to intervention groups, until the moment of assignment." Randomization without allocation concealment is not reliable randomization.)

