## PROTOCOL SUMMARY

[figure not shown]
Title	STILL 3 Study
Brief Summary	
The purpose is to provide further evidence concerning the efficacy of tACS for treatment of auditory hallucinations and to evaluate an exploratory maintenance stimulation paradigm to prolong the duration of stimulation-induced clinical benefits. We will study 40 eligible males and females diagnosed with schizophrenia or schizo-affective disorder. The longitudinal experimental design is a two-treatment, 4-sequence, multi-period randomized crossover design. During the first week, the enrolled participants will have 5, daily, 40-minute stimulation sessions. At the end of the first week, the participants will begin an 8-week maintenance regimen of weekly 40-minute stimulation sessions.
 
A randomization protocol will be used to assign each participant to either a sham regimen or an active regimen during the first week, and to a sham or active maintenance regimen. Equal numbers of participants will be assigned by random allocation to the four treatment-sequence groups: tACS-tACS, tACS-sham, sham-tACS, sham-sham.
 
Participation will involve 1 to 18 visits. At the initial phone session, informed consent will be obtained and subjects will be screened for eligibility. Participants will be contacted again in 2 weeks for a second phone screening session to determine stability of auditory hallucination symptoms, utilizing the Auditory Hallucinations Rating Scale (AHRS, attachment 3). If the AHRS scores are within <math>\pm 20\%</math> of their previous score, they will be considered eligible. If the AHRS scores do not fall within this range, participants will be rescheduled for a third or fourth screening session separated by 2 weeks. If, after the fourth screening session the participant does not have stable AHRS scores, they will not be eligible to participate.
 
Eligible participants will be scheduled for their daily stimulation sessions which will include a daily assessment of stimulation side-effects. Clinical assessments of auditory hallucinations will be administered with the AHRS and the self-administered Hamilton Program for Schizophrenia Voices (HPSVQ). These measurements will be assessed at the time of enrollment into the study (baseline), at the first day of stimulation, at the fifth day of stimulation, and once weekly for 8 weeks of maintenance stimulation sessions. Neurophysiological (EEG) and cognitive assays will be performed day 1 of stimulation, day 5 of stimulation, and at maintenance stimulation sessions for weeks 1, 3 and 8. In conjunction with

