## SCHEMATIC OF STUDY DESIGN

At enrollment, the 40 eligible enrollees will be allocated by randomization to four treatment-sequence groups: tACS-tACS, tACS-sham, sham-sham, sham-tACS) (10 participants per sequence). The randomization will be stratified by sex.

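### The stated equal allocation of 10 participants per sequence is not ensured by the randomization procedure in section 10.4.1

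*Combined protocol and SAP*

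**What the plan says.** The Protocol Summary states: "Equal numbers of participants will be assigned by random allocation to the four treatment-sequence groups". The Schematic of Study Design puts the figure at "10 participants per sequence", 40 in all, stratified by sex. Section 10.3 builds its precision statement on 20 participants per regimen in period 1.

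Section 10.4.1 describes the mechanism. "The codes will be randomized using a randomization function available in MATLAB software", and "separate randomization schedules will be created for each sex". On length: "A total of 40 codes will be randomized for each sex", because the split could be very uneven ("for example, 35 men and only 5 women"). One restriction is given: "A condition will be included so that the same condition will not be assigned to adjacent participants 3 times in a row". No block, block size or composition of the 40-code lists is stated anywhere.

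The primary model in section 10.2 has four mean parameters and the baseline score. It has no term for sex.

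**The concern.** Two lists of 40 make 80 codes, of which 40 are used. Each list stops wherever enrolment of that sex stops, so even a list holding 10 of each sequence is generally unbalanced at the point of truncation. A rule against three in a row limits runs but does not steer four sequence totals towards equality.

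At stake are a design property that the protocol states as fact and that the power calculation takes for granted, and the purpose of stratifying. Separate lists balance the sequences within each sex only if each list is itself restricted.

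**Working it through.** **Inputs.** 40 participants, four sequences and 10 each (Protocol Summary, Schematic); 40 codes per sex, the no-three-in-a-row rule and the 35/5 example (10.4.1); inter-subject variance 4.98 and intra-subject variance 0.55, summing to 5.53 (Table 2); difference 1.18 AHRS units, F-test at α = 0.025, stated power 90% [50%, 99%] (10.3).

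**1. The plan's own figure at 10 per sequence.** The model uses t1 and t9 with compound symmetry and no carryover.
- Correlation: 4.98 / 5.53 = 0.9005.
- Variance of the period-1 contrast: (2 × 5.53 / 20) × (1 − 0.9005²) = 0.553 × 0.189 = 0.1045, so SE = 0.323.
- 1.18 / 0.323 = 3.65. A noncentral F(1, 37) gives power 90.0%. The 37 degrees of freedom are my assumption; 35 to 38 give 89.9–90.1%.
- At the variance limits (12.35 and 1.37; 2.66 and 0.30), power is 49.7% and 99.4%.

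The stated figure reproduces under equal allocation.

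**2. What the procedure delivers.** I simulated 5,000 trials per setting. *Condition* is read as one of the four sequences, and codes are used in list order. Because 10.4.1 is silent on list make-up, two readings were run, both with the no-three-in-a-row rule: independent 1-in-4 draws, and a shuffle of a list holding 10 of each sequence. As a check, independent draws without the run rule give 40! / (10!⁴ × 4⁴⁰) = 0.39%. Two block schemes, without the run rule, are shown for comparison.

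| Split by sex | Independent: exactly 10 each | Independent: smallest ≤ 7 | Pre-balanced: exactly 10 each | Pre-balanced: smallest ≤ 7 | Blocks of 4: exactly 10 each | Blocks of 4 and 8: exactly 10 each |
|---|---|---|---|---|---|---|
| 40/0 | 0.7% | 55.8% | 100% | 0% | 100% | 74.1% |
| 35/5 | 0.5% | 56.4% | 4.4% | 5.1% | 24.7% | 17.6% |
| 30/10 | 0.6% | 56.7% | 2.3% | 19.1% | 16.5% | 12.7% |
| 28/12 | 0.5% | 55.4% | 2.1% | 22.5% | 100% | 52.8% |
| 25/15 | 0.6% | 54.9% | 1.5% | 24.9% | 25.1% | 18.8% |
| 20/20 | 0.4% | 56.5% | 1.6% | 28.7% | 100% | 54.3% |

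**3. Why blocks of 4 bound the counts.** At 35/5, the men fill 8 blocks plus 3 codes and the women 1 block plus 1 code. Every sequence therefore has at least 8 + 1 = 9 and at most 11. All reach 10 only if the one extra woman falls in the sequence that the men's part-block missed, which has chance 1/4. At 30/10 each sex has two left-over codes, and they must be complementary pairs: 1/6. With blocks of 4 and 8, counts stayed within 8–12 at 35/5, 28/12, 25/15 and 20/20. At 30/10 they reached 7 and 13, with a smallest group of 7 or fewer in 0.1% of trials.

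**4. Effect on the planned test.**
- Independent draws: mean power 88.8%, 5th percentile about 86%.
- Pre-balanced lists with both sexes enrolling: mean 89.4–89.8%, 5th percentile 88–89%.
- Either block scheme: mean 89.9–90.0%.
- Single examples, in the order SS, SA, AS, AA: 7, 9, 11, 13 gives 88.7%; 6, 8, 12, 14 gives 86.8%.

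**5. Effect on the period-1 margin of error.** At 20 per regimen it is 1.96 × 2.35 / √20 = 1.03 AHRS units, against the plan's figure of about 1.0. A 17/23 split gives 1.12 in the smaller regimen (4.606 / √17) and 0.96 in the larger (4.606 / √23). An imbalance of that size or worse occurs in about 37% of trials with independent draws, and in 5–21% with pre-balanced lists and both sexes.

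**The case against.** The strongest reply is that this hardly matters to the analysis. Average power moves by about one point or less, while the protocol's own uncertainty about it runs from 50% to 99%. Section 10.2 also drops participants who do not complete, so exact balance at randomization would not survive to the analysed set. Both statements are correct and limit the weight of the point.

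Three stronger readings are tempting and are not supported.
- *The lists are unblocked and cannot give 10 per sequence.* Section 10.4.1 does not mention blocks, but it does not exclude them. Exact balance can also arise by chance, and with pre-balanced lists it is certain if only one sex enrols. The documents support *does not ensure*.
- *Permuted blocks would deliver exactly 10 each at no cost.* At the protocol's own 35/5 example, blocks of 4 do so about a quarter of the time and mixed blocks less often. Small blocks also make later codes more predictable once earlier ones are known, and section 10.4.3 lets the PI learn a participant's condition after an AE or SAE.
- *Imbalance undermines the maintenance question through a tACS-tACS versus tACS-sham comparison.* Section 10.2 plans no such contrast. In the primary model, with carryover set to zero, the period-2 mean depends only on the period-2 treatment.

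What remains is that two sections state an allocation that the described mechanism does not secure.

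**Conclusion.** The point holds as a mismatch between a stated design property and the stated procedure. With both sexes enrolled, exactly 10 per sequence would be rare under either reading of the lists, and a group of 7 or fewer would be common with independent draws and possible with pre-balanced ones. The consequence for the primary test is small: a loss of about one point of power on average, and about four points at the 5th percentile in the less favourable reading.

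This rests on reading *condition* as a sequence, on codes being used in list order, on the Table 2 variance components, and on 10.4.1 being complete as to restrictions. If the lists were in fact blocked, the gap is one of reporting. The power figures concern the separate test of the period-1 difference used in section 10.3, not the joint F-test. The effect of adding sex to the model was not calculated.

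**What to change.** 1. In section 10.4.1, state that each sex's list is generated in random permuted blocks containing all four sequences equally, with block sizes withheld from site staff. Blocks of 4 hold every sequence at 9–11. Mixed blocks of 4 and 8 hold it at about 8–12 and are harder to predict. Neither guarantees 10 unless the sex totals happen to fit.
2. Say whether the no-three-in-a-row rule stays. Blocks of 4 meet it automatically, since the longest run of one sequence is two; blocks of 8 need not.
3. In the Protocol Summary and the Schematic, replace the promise of equality with *approximately 10 per sequence*.
4. In section 10.2, add sex, the stratification factor, as a fixed effect in the primary model.
5. If codes have already been issued, apply the change to unused codes only and report how the lists were built.

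The cost is a few lines in the list-generating script, one model term and some wording. It needs no additional participants and changes no participant procedure. The trade-off is between predictability and balance: varying the block sizes lowers the first and slightly loosens the second.
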